## Urinary

PARAMETER	GRADE 1 MILD	GRADE 2 MODERATE	GRADE 3 SEVERE	GRADE 4 POTENTIALLY LIFE- THREATENING
Urinary Tract Obstruction	NA	Signs or symptoms of urinary tract obstruction without hydronephrosis or renal dysfunction	Signs or symptoms of urinary tract obstruction with hydronephrosis or renal	Obstruction causing life-threatening consequences

## Site Reactions to Injections and Infusions

PARAMETER	GRADE 1 MILD	GRADE 2 MODERATE	GRADE 3 SEVERE	GRADE 4 POTENTIALLY LIFE- THREATENING
Injection Site Pain or Tenderness Report only one	Pain or tenderness causing no or minimal limitation of use of limb	Pain or tenderness causing greater than minimal limitation of use of limb	Pain or tenderness causing inability to perform usual social & functional activities	Pain or tenderness causing inability to perform basic self-care function OR Hospitalization indicated
Injection Site Erythema or Redness  Report only one > 15 years of age	2.5 to < 5 cm in diameter OR 6.25 to < 25 cm  surface area AND Symptoms causing no or minimal interference with usual social & functional activities	≥ 5 to < 10 cm in diameter OR ≥ 25 to < 100 cm  surface area OR Symptoms causing greater than minimal interference with usual social & functional activities	≥ 10 cm in diameter OR ≥ 100 cm  surface area OR Ulceration OR Secondary infection OR Phlebitis OR Sterile abscess OR Drainage OR Symptoms causing inability to perform usual	Potentially life-threatening consequences (e.g., abscess, exfoliative dermatitis, necrosis involving dermis or deeper tissue)

PARAMETER	GRADE 1 MILD	GRADE 2 MODERATE	GRADE 3 SEVERE	GRADE 4 POTENTIALLY LIFE- THREATENING
$\leq 15$ years of age	$\leq 2.5$ cm in diameter	$> 2.5$ cm in diameter with $< 50\%$ surface area of the extremity segment involved (e.g., upper arm or thigh)	$\geq 50\%$ surface area of the extremity segment involved (e.g., upper arm or thigh) OR Ulceration OR Secondary infection OR Phlebitis OR Sterile abscess OR Drainage	Potentially life-threatening consequences (e.g., abscess, exfoliative dermatitis, necrosis involving dermis or deeper tissue)
Injection Site Induration or Swelling Report only one > 15 years of age	Same as for Injection Site Erythema or Redness, > 15 years of age	Same as for Injection Site Erythema or Redness, > 15 years of age	Same as for Injection Site Erythema or Redness, > 15 years of age	Same as for Injection Site Erythema or Redness, > 15 years of age
$\leq 15$ years of age	Same as for Injection Site Erythema or Redness, <math>\leq 15</math> years of age	Same as for Injection Site Erythema or Redness, <math>\leq 15</math> years of age	Same as for Injection Site Erythema or Redness, <math>\leq 15</math> years of age	Same as for Injection Site Erythema or Redness, <math>\leq 15</math> years of age
Injection Site Pruritus	Itching localized to the injection site that is relieved spontaneously or in $< 48$ hours of treatment	Itching beyond the injection site that is not generalized OR Itching localized to the injection site requiring $\geq 48$ hours	Generalized itching causing inability to perform usual social & functional activities	NA
13. Injection Site Erythema or Redness should be evaluated and graded using the greatest single diameter or measured surface area.				

### Laboratory Values

#### Chemistries

PARAMETER	GRADE 1 MILD	GRADE 2 MODERATE	GRADE 3 SEVERE	GRADE 4 POTENTIALLY LIFE- THREATENING
Acidosis	NA	$\text{pH} \geq 7.3$ to $< \text{LLN}$	$\text{pH} < 7.3$ without life-threatening consequences	$\text{pH} < 7.3$ with life-threatening consequences

PARAMETER	GRADE 1 MILD	GRADE 2 MODERATE	GRADE 3 SEVERE	GRADE 4 POTENTIALLY LIFE-THREATENING
Albumin, Low (g/dL; g/L)	3.0 to < LLN 30 to < LLN	≥ 2.0 to < 3.0 ≥ 20 to < 30	< 2.0 < 20	NA
Alkaline Phosphatase, High	1.25 to < 2.5 x ULN	2.5 to < 5.0 x ULN	5.0 to < 10.0 x ULN	≥ 10.0 x ULN
Alkalosis	NA	pH > ULN to ≤ 7.5	pH > 7.5 without life-threatening consequences	pH > 7.5 with life-threatening consequences
ALT or SGPT, High Report only one	1.25 to < 2.5 x ULN	2.5 to < 5.0 x ULN	5.0 to < 10.0 x ULN	≥ 10.0 x ULN
Amylase (Pancreatic) or Amylase (Total), High Report only one	1.1 to < 1.5 x ULN	1.5 to < 3.0 x ULN	3.0 to < 5.0 x ULN	≥ 5.0 x ULN
AST or SGOT, High Report only one	1.25 to < 2.5 x ULN	2.5 to < 5.0 x ULN	5.0 to < 10.0 x ULN	≥ 10.0 x ULN
Bicarbonate, Low (mEq/L; mmol/L)	16.0 to < LLN 16.0 to < LLN	11.0 to < 16.0 11.0 to < 16.0	8.0 to < 11.0 8.0 to < 11.0	< 8.0 < 8.0
Bilirubin Direct Bilirubin, High > 28 days of age	NA	NA	> ULN	> ULN with life-threatening consequences (e.g., signs and symptoms of liver failure)
≤ 28 days of age	ULN to ≤ 1 mg/dL	> 1 to ≤ 1.5 mg/dL	> 1.5 to ≤ 2 mg/dL	> 2 mg/dL
Total Bilirubin, High > 28 days of age	1.1 to < 1.6 x ULN	1.6 to < 2.6 x ULN	2.6 to < 5.0 x ULN	≥ 5.0 x ULN
Calcium, High (mg/dL; mmol/L) ≥ 7 days of age	10.6 to < 11.5 2.65 to < 2.88	11.5 to < 12.5 2.88 to < 3.13	12.5 to < 13.5 3.13 to < 3.38	≥ 13.5 ≥ 3.38
< 7 days of age	11.5 to < 12.4 2.88 to < 3.10	12.4 to < 12.9 3.10 to < 3.23	12.9 to < 13.5 3.23 to < 3.38	≥ 13.5 ≥ 3.38
Calcium (Ionized), High (mg/dL; mmol/L)	> ULN to < 6.0 > ULN to < 1.5	6.0 to < 6.4 1.5 to < 1.6	6.4 to < 7.2 1.6 to < 1.8	≥ 7.2 ≥ 1.8
Calcium, Low (mg/dL; mmol/L)				

PARAMETER	GRADE 1 MILD	GRADE 2 MODERATE	GRADE 3 SEVERE	GRADE 4 POTENTIALLY LIFE- THREATENING
$\geq 7$ days of age	7.8 to < 8.4 1.95 to < 2.10	7.0 to < 7.8 1.75 to < 1.95	6.1 to < 7.0 1.53 to < 1.75	< 6.1 < 1.53
< 7 days of age	6.5 to < 7.5 1.63 to < 1.88	6.0 to < 6.5 1.50 to < 1.63	5.50 to < 6.0 1.38 to < 1.50	< 5.50 < 1.38
Calcium (Ionized), Low (mg/dL; mmol/L)	< LLN to 4.0 < LLN to 1.0	3.6 to < 4.0 0.9 to < 1.0	3.2 to < 3.6 0.8 to < 0.9	< 3.2 < 0.8
Cardiac Troponin I, High	NA	NA	NA	Levels consistent with myocardial infarction or unstable angina as defined by the local laboratory
Creatine Kinase, High	3 to < 6 x ULN	6 to < 10 x ULN	10 to < 20 x ULN	$\geq 20$ x ULN
Creatinine, High	1.1 to 1.3 x ULN	> 1.3 to 1.8 x ULN OR Increase of > 0.3 mg/dL above baseline	> 1.8 to < 3.5 x ULN OR Increase of 1.5 to < 2.0 x above baseline	$\geq 3.5$ x ULN OR Increase of $\geq 2.0$ x above baseline
Creatinine Clearance 15 or eGFR, Low Report only one	NA	< 90 to 60 ml/min or ml/min/1.73 m  OR 10 to < 30% decrease from baseline	< 60 to 30 ml/min or ml/min/1.73 m  OR $\geq 30$ to < 50% decrease from baseline	< 30 ml/min or ml/min/1.73 m  OR $\geq 50\%$ decrease from baseline or dialysis needed
Glucose (mg/dL; mmol/L)				
Fasting, High	110 to 125 6.11 to < 6.95	> 125 to 250 6.95 to < 13.89	> 250 to 500 13.89 to < 27.75	> 500 $\geq 27.75$
Nonfasting, High	116 to 160 6.44 to < 8.89	> 160 to 250 8.89 to < 13.89	> 250 to 500 13.89 to < 27.75	> 500 $\geq 27.75$
Glucose, Low (mg/dL; mmol/L)				
$\geq 1$ month of age	55 to 64 3.05 to 3.55	40 to < 55 2.22 to < 3.05	30 to < 40 1.67 to < 2.22	< 30 < 1.67
< 1 month of age	50 to 54 2.78 to 3.00	40 to < 50 2.22 to < 2.78	30 to < 40 1.67 to < 2.22	< 30 < 1.67
Lactate, High	ULN to < 2.0 x ULN without acidosis	$\geq 2.0$ x ULN without acidosis	Increased lactate with pH < 7.3 without life-threatening consequences	Increased lactate with pH < 7.3 with life-threatening consequences

PARAMETER	GRADE 1 MILD	GRADE 2 MODERATE	GRADE 3 SEVERE	GRADE 4 POTENTIALLY LIFE-THREATENING
Lipase, High	1.1 to < 1.5 x ULN	1.5 to < 3.0 x ULN	3.0 to < 5.0 x ULN	≥ 5.0 x ULN
Lipid Disorders (mg/dL; mmol/L)				
Cholesterol, Fasting, High ≥ 18 years of age	200 to < 240 5.18 to < 6.19	240 to < 300 6.19 to < 7.77	≥ 300 ≥ 7.77	NA
< 18 years of age	170 to < 200 4.40 to < 5.15	200 to < 300 5.15 to < 7.77	≥ 300 ≥ 7.77	NA
LDL, Fasting, High ≥ 18 years of age	130 to < 160 3.37 to < 4.12	160 to < 190 4.12 to < 4.90	≥ 190 ≥ 4.90	NA
> 2 to < 18 years of age	110 to < 130 2.85 to < 3.34	130 to < 190 3.34 to < 4.90	≥ 190 ≥ 4.90	NA
Triglycerides, Fasting, High	150 to 300 1.71 to 3.42	>300 to 500 >3.42 to 5.7	>500 to < 1,000 >5.7 to 11.4	> 1,000 > 11.4
Magnesium^16, Low (mEq/L; mmol/L)	1.2 to < 1.4 0.60 to < 0.70	0.9 to < 1.2 0.45 to < 0.60	0.6 to < 0.9 0.30 to < 0.45	< 0.6 < 0.30
Phosphate, Low (mg/dL; mmol/L)				
> 14 years of age	2.0 to < LLN 0.81 to < LLN	1.4 to < 2.0 0.65 to < 0.81	1.0 to < 1.4 0.32 to < 0.65	< 1.0 < 0.32
1 to 14 years of age	3.0 to < 3.5 0.97 to < 1.13	2.5 to < 3.0 0.81 to < 0.97	1.5 to < 2.5 0.48 to < 0.81	< 1.5 < 0.48
< 1 year of age	3.5 to < 4.5 1.13 to < 1.45	2.5 to < 3.5 0.81 to < 1.13	1.5 to < 2.5 0.48 to < 0.81	< 1.5 < 0.48
Potassium, High (mEq/L; mmol/L)	5.6 to < 6.0 5.6 to < 6.0	6.0 to < 6.5 6.0 to < 6.5	6.5 to < 7.0 6.5 to < 7.0	≥ 7.0 ≥ 7.0
Potassium, Low (mEq/L; mmol/L)	3.0 to < 3.4 3.0 to < 3.4	2.5 to < 3.0 2.5 to < 3.0	2.0 to < 2.5 2.0 to < 2.5	< 2.0 < 2.0
Sodium, High (mEq/L; mmol/L)	146 to < 150 146 to < 150	150 to < 154 150 to < 154	154 to < 160 154 to < 160	≥ 160 ≥ 160
Sodium, Low (mEq/L; mmol/L)	130 to < 135 130 to < 135	125 to < 130 125 to < 135	121 to < 125 121 to < 125	≤ 120 ≤ 120
Uric Acid, High (mg/dL; mmol/L)	7.5 to < 10.0 0.45 to < 0.59	10.0 to < 12.0 0.59 to < 0.71	12.0 to < 15.0 0.71 to < 0.89	≥ 15.0 ≥ 0.89
14. Direct bilirubin > 1.5 mg/dL in a participant < 28 days of age should be graded as grade 2, if < 10% of the total bilirubin.				
15. Use the applicable formula (i.e., Cockcroft-Gault in mL/min or Schwartz in mL/min/1.73m  ).				

PARAMETER	GRADE 1 MILD	GRADE 2 MODERATE	GRADE 3 SEVERE	GRADE 4 POTENTIALLY LIFE- THREATENING
16. To convert a magnesium value from mg/dL to mmol/L, laboratories should multiply by 0.4114				

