#### **7.4.2. Laboratory Assessments**

All protocol required laboratory assessments, as defined in the Time and Events Schedule (see Section 7.1), must be performed by the central laboratory. Laboratory assessments must be conducted in accordance with the Central Laboratory Manual and Protocol Time and Events Schedule. Laboratory requisition forms must be completed and samples must be clearly labeled with the participant number, protocol number, site/centre number, and visit date. Details for the preparation and shipment of samples will be provided by the central laboratory. Reference ranges for all safety parameters will be provided to the site by the central laboratory.

If additional non-protocol specified laboratory assessments are performed at the institution's local laboratory and result in a change in subject management or are considered clinically significant by the investigator (e.g., SAE or AE or dose modification) the results must be recorded in the eCRF. Local laboratory services may be used to verify pending laboratory parameters only after consultation and agreement with the study team.

Refer to the lab manual for appropriate processing and handling of samples to avoid duplicate and/or additional blood draws.

Labs will be automatically graded by the central lab according to the DAIDS toxicity scales (See Section 12.2 "Division of AIDS Table for Grading the Severity of Adult and Pediatric Adverse Events").

For fasting laboratory assessments, an overnight fast is preferred; however, a minimum of a 6 hour fast is acceptable.

Table 6 includes lab parameters to be assessed as per the Time and Events Schedule (see Section 7.1):

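### Appendix 2: two of three adult low-phosphate cut-offs and one low-sodium cell disagree between units, so the grade depends on an unnamed unit

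*Protocol*

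**What the plan says.** Appendix 2 (Section 12.2) reproduces the DAIDS grading table, version 2.0. In the Chemistries block each cell gives the conventional unit first and the SI unit second. For low phosphate above 14 years of age the cells are:

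- Grade 1: "2.0 to < LLN 0.81 to < LLN"
- Grade 2: "1.4 to < 2.0 0.65 to < 0.81"
- Grade 3: "1.0 to < 1.4 0.32 to < 0.65"
- Grade 4: below 1.0 mg/dL, or below 0.32 mmol/L.

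The row beneath, for ages 1 to 14, has "3.0 to < 3.5 0.97 to < 1.13" for Grade 1 and "2.5 to < 3.0 0.81 to < 0.97" for Grade 2.

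For low sodium (mEq/L, then mmol/L), Grade 1 is "130 to < 135 130 to < 135" and Grade 2 is "125 to < 130 125 to < 135".

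On use of the table, Section 7.4.2 states: "Labs will be automatically graded by the central lab according to the DAIDS toxicity scales". It names no unit. Phosphate and sodium are both in the chemistry panel (Table 6), and inclusion criterion 1 makes every participant an adult. Section 9.4.2 tabulates graded laboratory toxicities by treatment group and by baseline third agent class. Sections 7.4.3.10 and 7.4.3.11 handle Grade 1 or 2 and Grade 3 events differently.

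**The concern.** Two columns that express one threshold in two units should give the same grade to the same blood sample. In the adult phosphate row 0.81 mmol/L sits beside 2.0 mg/dL, while in the row directly below the same 0.81 mmol/L sits beside 2.5 mg/dL. Both cannot be right. In the sodium row the two units are numerically identical, yet the Grade 2 upper limits differ by 5.

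The affected phosphate row is the one that applies to this trial. Incidence and severity of laboratory abnormalities is a secondary safety endpoint, and one of the affected boundaries separates Grade 2 from Grade 3, where the protocol's handling changes. If the grading program was built from this appendix, the reported severity depends on which column was coded.

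**Working it through.** **Step 1: the phosphate factor, from the table itself.** The two paediatric rows give five distinct pairs:

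| mg/dL | mmol/L | ratio |
|---|---|---|
| 1.5 | 0.48 | 0.320 |
| 2.5 | 0.81 | 0.324 |
| 3.0 | 0.97 | 0.3233 |
| 3.5 | 1.13 | 0.3229 |
| 4.5 | 1.45 | 0.3222 |

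The mmol/L figures are rounded to two decimals, so a factor fits all five pairs only between (0.81 − 0.005)/2.5 = 0.3220 and (0.48 + 0.005)/1.5 = 0.3233. The molar-mass factor, 10/30.974 = 0.3229, lies inside that range.

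**Step 2: apply it to the adult row.**

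| mg/dL cut-off | printed mmol/L | implied factor | mg/dL × 0.3229 | printed mmol/L ÷ 0.3229 |
|---|---|---|---|---|
| 2.0 | 0.81 | 0.405 | 0.65 | 2.51 mg/dL |
| 1.4 | 0.65 | 0.464 | 0.45 | 2.01 mg/dL |
| 1.0 | 0.32 | 0.320 | 0.32 | 0.99 mg/dL |

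Only the third pair is reproduced. The first two are too far out for rounding to explain.

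**Step 3: grade the same sample in both columns.** The documents give no lower limit of normal (LLN) for phosphate, so it is assumed here at 2.0, 2.2, 2.5, 2.7 and 3.0 mg/dL. Samples are taken in steps of 0.1 mg/dL, with mmol/L rounded to two decimals.

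| Sample (mg/dL) | Same sample (mmol/L) | Grade by mg/dL | Grade by mmol/L |
|---|---|---|---|
| 1.4 to 1.9 | 0.45 to 0.61 | 2 | 3 |
| 2.0 to 2.4, LLN 2.5 or higher | 0.65 to 0.77 | 1 | 2 |
| from an LLN of 2.0 or 2.2 up to 2.4 | up to 0.77 | none | 2 |

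The first line does not depend on the LLN. Where the columns disagree, the mmol/L column gives the higher grade. Without rounding, exactly 2.0 mg/dL is 0.646 mmol/L, which falls just under 0.65 and so into Grade 3 of that column. Below 1.4 mg/dL the two columns agree in this check.

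**Step 4: sodium.** Sodium is monovalent, so 1 mEq/L = 1 mmol/L, and the high-sodium row prints the same figures in both units. In mEq/L, 130 to 134 is Grade 1 only. In mmol/L the same values meet Grade 1 (130 to below 135) and also Grade 2 (125 to below 135). From 125 to 129 both columns give Grade 2. The defect is one cell, and it creates an overlap within a column.

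**The case against.** The strongest reply is that the appendix reproduces an external standard. Section 7.4.2 sends all protocol-required laboratory work to one central laboratory, which grades by that standard. If its program uses one unit set throughout, both arms face the same cut-offs. If that set is mg/dL and mEq/L, nothing changes in practice. All of this stands, and it limits the consequence. It does not remove the contradiction, because the protocol names no unit, and without the source table no one can tell from the documents whether the slip lies in the source or in the copy.

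Three stronger readings are tempting, and the documents do not support them.

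- A reader might infer a bias between arms. Nothing indicates that participants, sites or arms are graded in different units, and the grade summaries in Section 9.4.2 are descriptive.
- A reader might infer that the tubular-dysfunction definition in Section 7.4.4.7.1 shifts. It uses a fixed serum phosphate value in mg/dL, not a grade, so the mismatch cannot alter it.
- A reader might infer that a higher grade automatically stops treatment. Section 7.4.3.11 ties withholding to events judged related or possibly related. Asymptomatic Grade 3 laboratory abnormalities have their own route of investigation and discussion with the Medical Monitor.

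It is also fair to say that the sodium cell looks like a simple misprint and leaves values ambiguous without raising them by a definite grade.

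**Conclusion.** The point holds as an internal contradiction in thresholds that the trial uses. Two of the three adult low-phosphate cut-offs disagree between units, and one low-sodium cell overlaps its neighbour. For phosphate the difference is one grade from 1.4 to below 2.0 mg/dL, whatever the LLN. From about 2.0 to 2.5 mg/dL it is one grade if the LLN is at least about 2.5 mg/dL. If the LLN is lower, results between it and about 2.5 mg/dL move from ungraded to Grade 2. Grade 4 phosphate is unaffected.

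What is at stake is the absolute severity reported for these analytes and whether the Grade 3 review steps are reached. The number of participants affected cannot be stated: the documents give no phosphate or sodium distribution, and any percentage would be set by the assumptions behind it. The conclusion rests on the table's own paediatric pairs and on the equality of the two sodium units. It does not establish which column is the intended one.

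**What to change.** Check the adult low-phosphate row and the low-sodium Grade 2 cell against the source grading table that Appendix 2 cites, and make the two unit columns agree. State in Section 7.4.2 or Appendix 2 which single unit set governs grading for all participants. Confirm in writing that the central laboratory's grading program uses that set. If the source table carries the same mismatch, say so and record how it was resolved.

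The arithmetic equivalents of the conventional-unit columns (0.65 and 0.45 mmol/L for phosphate; 125 to below 130 mmol/L for sodium) are given here only to show the mismatch. They are not a proposal of which cut-offs should stand.

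The cost is a correction to two table rows, one added sentence and one query to the central laboratory. If its program is found to have used the other column, the affected grades would need to be re-derived from the stored numeric results.

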### Hematology

PARAMETER	GRADE 1 MILD	GRADE 2 MODERATE	GRADE 3 SEVERE	GRADE 4 POTENTIALLY LIFE- THREATENING
Absolute CD4+ Count, Low (cell/mm  ; cells/L)  > 5 years of age (not HIV infected)	300 to < 400 300 to < 400	200 to < 300 200 to < 300	100 to < 200 100 to < 200	< 100 < 100
Absolute Lymphocyte Count, Low (cell/mm  ; cells/L)  > 5 years of age (not HIV infected)	600 to < 650 $0.600 \times 10^9$ to < $0.650 \times 10^9$	500 to < 600 $0.500 \times 10^9$ to < $0.600 \times 10^9$	350 to < 500 $0.350 \times 10^9$ to < $0.500 \times 10^9$	< 350 < $0.350 \times 10^9$
Absolute Neutrophil Count (ANC), Low (cells/mm  ; cells/L)	800 to 1,000 $0.800 \times 10^9$ to $1.000 \times 10^9$	600 to 799 $0.600 \times 10^9$ to $0.799 \times$ $10^9$	400 to 599 $0.400 \times 10^9$ to $0.599 \times$ $10^9$	< 400 < $0.400 \times 10^9$
2 to 7 days of age	1,250 to 1,500 $1.250 \times 10^9$ to $1.500 \times 10^9$	1,000 to 1,249 $1.000 \times 10^9$ to $1.249 \times$ $10^9$	750 to 999 $0.750 \times 10^9$ to $0.999 \times$ $10^9$	< 750 < $0.750 \times 10^9$
≤ 1 day of age	4,000 to 5,000 $4.000 \times 10^9$ to $5.000 \times 10^9$	3,000 to 3,999 $3.000 \times 10^9$ to $3.999 \times$ $10^9$	1,500 to 2,999 $1.500 \times 10^9$ to $2.999 \times$ $10^9$	< 1,500 < $1.500 \times 10^9$
Fibrinogen, Decreased (mg/dL; g/L)	100 to < 200 $1.00$ to < $2.00$ OR 0.75 to < 1.00 x LLN	75 to < 100 $0.75$ to < $1.00$ OR ≥ 0.50 to < 0.75 x LLN	50 to < 75 $0.50$ to < $0.75$ OR 0.25 to < 0.50 x	< 50 < $0.50$ OR < 0.25 x LLN OR Associated with gross bleeding

PARAMETER	GRADE 1 MILD	GRADE 2 MODERATE	GRADE 3 SEVERE	GRADE 4 POTENTIALLY LIFE-THREATENING
Hemoglobin, Low (g/dL; mmol/L)  ≥ 13 years of age (male only)	10.0 to 10.9 6.19 to 6.76	9.0 to < 10.0 5.57 to < 6.19	7.0 to < 9.0 4.34 to < 5.57	< 7.0 < 4.34
≥ 13 years of age (female only)	9.5 to 10.4 5.88 to 6.48	8.5 to < 9.5 5.25 to < 5.88	6.5 to < 8.5 4.03 to < 5.25	< 6.5 < 4.03
57 days of age to < 13 years of age (male and female)	9.5 to 10.4 5.88 to 6.48	8.5 to < 9.5 5.25 to < 5.88	6.5 to < 8.5 4.03 to < 5.25	< 6.5 < 4.03
36 to 56 days of age	8.5 to 9.6 5.26 to 5.99	7.0 to < 8.5 4.32 to < 5.26	6.0 to < 7.0 3.72 to < 4.32	< 6.0 < 3.72
22 to 35 days of age (male and female)	9.5 to 11.0 5.88 to 6.86	8.0 to < 9.5 4.94 to < 5.88	6.7 to < 8.0 4.15 to < 4.94	< 6.7 < 4.15
8 to ≤ 21 days of age (male and female)	11.0 to 13.0 6.81 to 8.10	9.0 to < 11.0 5.57 to < 6.81	8.0 to < 9.0 4.96 to < 5.57	< 8.0 < 4.96
≤ 7 days of age (male and female)	13.0 to 14.0 8.05 to 8.72	10.0 to < 13.0 6.19 to < 8.05	9.0 to < 10.0 5.59 to < 6.19	< 9.0 < 5.59
INR, High (not on anticoagulation)	1.1 to < 1.5 x ULN	1.5 to < 2.0 x ULN	2.0 to < 3.0 x ULN	≥ 3.0 x ULN
Methemoglobin (% hemoglobin)	5.0 to < 10.0%	10.0 to < 15.0%	15.0 to < 20.0%	≥ 20.0%
PTT, High (not on anticoagulation)	1.1 to < 1.66 x ULN	1.66 to < 2.33 x ULN	2.33 to < 3.00 x ULN	≥ 3.00 x ULN
Platelets, Decreased (cells/mm  ; cells/L)	100,000 to < 124,999 100.000 x 10  to < 124.999 x 10 	50,000 to < 100,000 50.000 x 10  to < 100.000 x 10 	25,000 to < 50,000 25.000 x 10  to < 50.000 x	< 25,000 < 25.000 x 10 
PT, High (not on anticoagulation)	1.1 to < 1.25 x ULN	1.25 to < 1.50 x ULN	1.50 to < 3.00 x ULN	≥ 3.00 x ULN

PARAMETER	GRADE 1 MILD	GRADE 2 MODERATE	GRADE 3 SEVERE	GRADE 4 POTENTIALLY LIFE- THREATENING
WBC, Decreased (cells/mm  ; cells/L)				
> 7 days of age	2,000 to 2,499 2.000 x 10^9 to 2.499 x 10^9	1,500 to 1,999 1.500 x 10^9 to 1.999 x 10^9	1,000 to 1,499 1.000 x 10^9 to 1.499 x 10^9	< 1,000 < 1.000 x 10^9
≤ 7 days of age	5,500 to 6,999 5.500 x 10^9 to 6.999 x 10^9	4,000 to 5,499 4.000 x 10^9 to 5.499 x 10^9	2,500 to 3,999 2.500 x 10^9 to 3.999 x 10^9	< 2,500 < 2.500 x 10^9
17. Male and female sex are defined as sex at birth. The conversion factor used to convert g/dL to mmol/L is 0.6206 and is the most commonly used conversion factor. For grading hemoglobin results obtained by an analytic method with a conversion factor other than 0.6206, the result must be converted to g/dL using the appropriate conversion factor for the particular laboratory.				

### Urinalysis

PARAMETER	GRADE 1 MILD	GRADE 2 MODERATE	GRADE 3 SEVERE	GRADE 4 POTENTIALLY LIFE- THREATENING
Glycosuria (random collection tested by	Trace to 1+ or ≤ 250 mg	2+ or > 250 to ≤ 500 mg	> 2+ or > 500 mg	NA
Hematuria (not to be reported based on dipstick findings or on blood believed to be of menstrual origin)	6 to < 10 RBCs per high power field	≥ 10 RBCs per high power field	Gross, with or without clots OR With RBC casts OR Intervention	Life-threatening consequences
Proteinuria (random collection tested by dipstick)	1+	2+	3+ or higher	NA

### 12.3. Appendix 3: Liver Safety – Study Treatment Restart or Rechallenge Guidelines

#### VSLC GUIDELINES FOR DRUG RESTART OR RECHALLENGE AFTER STOP FOR LIVER CRITERIA

**Drug Rechallenge** refers to resuming study treatment following drug induced liver injury (DILI). Because of the risks associated with rechallenge after DILI (see Drug Rechallenge Background below) this should only be considered for a participant for whom there is compelling evidence of benefit from a critical or life-saving medicine, there is no alternative approved medicine available, and a benefit:risk assessment of rechallenge is considered to be favorable (Table 14, Figure 9).

**Drug Restart** refers to resuming study treatment following liver events meeting stopping criteria **in which there is a clear underlying cause (other than DILI) of the liver event (e.g., biliary obstruction, pancreatic events, hypotension, acute viral hepatitis)**. Furthermore, there should be no evidence of alcoholic hepatitis or hypersensitivity, and the drug should not be associated with HLA markers of liver injury. (Table 15; Figure 10).

**As this determination can be difficult, for the purpose of these guidelines, cases should be treated as rechallenges if there is any reasonable likelihood that the liver event is related to study drug. Restarts should be limited to cases in which there is clear evidence that the underlying cause of the liver event is not related to study drug.**

